### 8.2 EFFICACY ASSESSMENTS

1. Salt/Placebo Intervention: Capsules will be dispensed by Clinical Center Pharmacy.
2. Flow Activating Cell Sorting (FACS) Analysis: Characterization of Leukocytes  
Populations : As part of assessing the whole blood epigenome and transcriptome, the protocol will perform an in-depth characterization of the heterogeneous mixture of leukocytes circulating in the blood and how this profile might be altered in response to the dietary sodium intervention. We will utilize the NHLBI's Flow Cytometry Core in collaboration with [name]. We will collect peripheral blood samples at the 4 time points (visit 1, 2 3 and 4). The FACS analysis will define changes in immune cell-type profiles as well as facilitate the isolation of DNA/RNA from specific immune cell sub-types (e.g. CD4 T-cells; CD8 T-cells, Monocytes etc.) for epigenome and transcriptome analysis.
3. Vascular function testing: These tests will be done using specialized non-invasive machines, such as SphygmoCor and EndoPAT, to assess vascular health.
4. 24-hour ambulatory blood pressure monitoring: Participants will be given an ambulatory blood pressure monitoring device that will be worn for 24 hours within two days of NIH baseline visit and again for 24 hours within two days prior to the return visits.
5. A 24-hour dietary recall will be administered at baseline and at each subsequent visit to assess differential diet and salt intake among each participant. Nutrition staff from the Clinical Center will meet with each participant and ask them to recall any foods or beverages they have eaten over the past 24 hours using an automated dietary analysis software application developed by the US Department of Agriculture for use in the National Health and Nutrition Examination Survey. The intakes for 108 nutrients (including salt) will be calculated for each participant based on individual diet.
6. Psychophysical Taste Task: Sucrose and Salt Detection Thresholds: Sucrose and salt detection thresholds will be assessed using a two-alternative forced-choice staircase procedure

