**Blood samples:**

Fasting samples for clinical chemistries:

Blood samples:

Clinical Center Research Lab Test					
Lab test	Volume Tube (ml)	Number of Tubes	Total Volume (ml)	Total Volume (tablespoon)	Tube type
CBC: CBC with differential count					
HbA1C: A1C	4	2	8	0.54	Lavender
Homocysteine					
Fasting lipid panel (serum):					
Mineral panel	3.5	2	7	0.47	green/yellow
Acute Care Panel					

GENE-FORECAST SIT  
29JUL2024

Total Protein ApoA1 and ApoB: APOAB Pro-BNP: BNP1 C-reactive protein: CRPHS (high sensitivity CRP)					
Hepatic Panel Serum hCG	3.5	1	3.5	0.24	Gold
Serum Cortisol (CORT)  Serum Aldosterone (ALD03,ADS01, ADS02)	8.5	1	8.5	0.57	Red SST
Clinical Center Research Labs Total	19.5	6	27	1.83	

Non-Clinical Center Research Lab Test					
Lab test	Volume Tube (ml)	Number of Tubes	Total Volume (ml)	Total Volume (tablespoon)	Tube type
DNA isolation (research, whole blood)	4	1	4	0.27	Lavender/EDTA
RNA/miRNA isolation (whole blood)	2.5	2	5	0.34	PaxGene
Plasma for research archiving	4	1	4	0.27	Green/ Lithium Heparin
Research tube for specialized endothelial function markers (e.g. VCAM-1, VEGF)	3.5	1	3.5	0.24	Red SST

Research tube for specialized inflammatory markers (e.g. IL6, TNF alpha)					
Plasma Renin Activity (PRA, PRAK1)	4	1	1	0.20	Lavendar/EDTA
Serum for research archiving	3.5	1	3.5	0.24	Red SST
FACS Analysis	10	4	40	2.71	Green/ Sodium Heparin
Non-Clinical Center Research Labs Total	27.5	10	60	4.06	
Total per visit (4 visits)	47	16	87	5.88	

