### **8.2.4 Samples for Genetic/Genomic Analysis**

#### **8.2.4.1 Description of the scope of genetic/genomic analysis**

- Analyses will include whole blood epigenetics based on DNA methylation and transcriptomics analysis will use whole blood and urine based on RNAseq.
- Germline and/or somatic analysis will not be conducted.
- Whole blood and urine will be the biospecimens used for analyses. Privacy and confidentiality of medical information/biological specimens will be maximized.
- No personal identifier will be maintained – including protected health information (PHI). Rather, participant will be assigned a unique numerical personal study identifier resulting in the unlikely occurrence of potential identification.
- Clinical and demographic information will be collected on each participant. Participant nor family members can be identified due to the use of a numerical personal study identifier.
- All coded participant, demographic, survey, medical and biological information will be stored in a medical file and a secured NIH database with appropriate IT security measures (e.g. de- identified codes; encryption; password access protection) to maximize the protection of privacy. Only the database manager will have access to the password key for code.
- Pedigree information will not be published.
- The personal identifier will not be released to any third party.
- No personal identifier containing data/sample information will be shared with other investigators. Information will only be deposited into a relevant controlled access database as mandated by NIH policies.
- For additional protection of confidentiality, all hard-copy information will be maintained in a locked file-cabinet with access only by the Research Nurse and Data-Base manager. Hard-copy information will be maintained and destroyed based on the duration mandated by NIH policies. In addition, we will use a custom designed NIH database - Clinical Trial Data Base (CTDB) designed for the collection and storage of study indices from study participants. Access to study participants' information is limited to only a few of the investigators and support staff. The database has password protection, stratified access, and firewall protection.

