#### 9.4.3 Analysis of the Secondary Endpoint(s)

The secondary endpoints will be assessed independent of the results associated with the primary endpoints; secondary endpoints include blood pressure, whole blood epigenome, and whole blood and urine transcriptome. The effect of treatment and placebo will be investigated will be investigated for each secondary endpoint, as detailed below.

The association between blood pressure (systolic and diastolic) and salt intake will be assessed using multiple linear regression with salt intake (two categories: treatment and placebo) as the exposure variable and blood pressure outcome variable. The effect size, p-value and 95% confidence interval of the regression model will be provided as results.

The effect of salt intake on gene expression will be investigated in a differential expression analysis to identify genes whose expression differs significantly between treatment and placebo. The gene expression data will be normalized, using the weighted trimmed mean of M-values (TMM) method, an optimal method for the normalization of mRNA count data. Genes with an expression less than 1 Count Per Million (CPM = count/sum [counts] x 1million) in at least 2 samples will be excluded because results from genes with extremely low expression are not reliable. Gene expression is generated as count data which follows a Poisson distribution; therefore, a negative binomial model will be fitted using the R library *edgeR* developed to handle the specificities of mRNA sequencing data. The model computes likelihood ratio tests for the coefficients whilst taking into account dispersion. A deviance of goodness of fit test will be carried out to identify genes where the model fit was poor indicating that the dispersion estimate is away from the average dispersion. Dispersion outliers will not be considered for the results because the deviance indicates low quality or marked expression difference for the gene. Finally, genes with a log fold change not equal to 0 and a false discovery rate adjusted p-value  $\leq 0.05$  will be reported as significantly differentially expressed between treatment and placebo. Multiple testing correction, for the total number of genes considered, will be carried out using the Benjamini-Hochberg method.

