The epigenetic effect of salt intake will be investigated through a two-sample t-test to identify methylation sites with significant methylation level difference between treatment and placebo. At a minimum of 5X coverage and an average coverage of 30X, the SureSelect-MethSeq (SS-Methseq) platform captures between 2.6 and 2.3 million methylation sites. After thorough processing and QC of the methylation data, using the Bismark pipeline, samples and methylation sites that passed all QC filters will be considered for the analysis. Each methylation site will be treated as a continuous variable and salt intake will be treated as a nominal variable with two categories (treatment and placebo), in the t-test. In such analysis, the methylation sites are assumed to be independent and there is, hence, a high burden of multiple testing due to the millions of sites being tested. Therefore, a significance threshold of p-value  $< 9 \times 10^{-8}$  will be applied to control for false positive findings; this threshold was derived from empirical work based on the Illumina EPIC array which has a lower density than the SS-Methseq platform but includes carefully selected sites that span the whole genome. The estimated mean difference, p-value and 95% confidence interval of the t-test will be presented as the results.

After the transcriptome, epigenome and microbiome data have been considered separately in the analyses described above and to understand the links between gene expression and methylation, an ensemble technique such as Random Forests will be used to leverage the high dimensionality of the data (number of features >> number of observations) and identify the best combination of predictors of salt intake in the transcriptome and epigenome data. Subsequently, the OTUs identified in the microbiome data will be integrated to find out if microbiome information improves the prediction accuracy of the omics data. This will provide further insights into the interplay between the three domains (microbiome, transcriptome and epigenome).

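### Whole-blood methylation and RNA-seq are compared by treatment alone, although the leukocyte mix is measured at every visit, so a shift in cell mix could be read as a change within cells

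*Combined protocol and SAP*

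**What the plan says.** **Measurement.** Section 8.2, item 2, plans FACS on blood from visits 1 to 4 as part of assessing the whole-blood epigenome and transcriptome. Its stated purpose is an "in-depth characterization of the heterogeneous mixture of leukocytes circulating in the blood and how this profile might be altered in response" to the sodium intervention. The same item says that FACS will help to isolate DNA and RNA from particular immune cell subtypes. The blood table in section 8.2.2 also lists "CBC: CBC with differential count", and FACS takes 40 of the 87 ml drawn per visit.

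**Analysis.** For methylation, section 9.4.3 says: "The epigenetic effect of salt intake will be investigated through a two-sample t-test to identify methylation sites". It adds that "salt intake will be treated as a nominal variable with two categories (treatment and placebo), in the t-test", and sets a threshold of p < 9 × 10⁻⁸. For expression, "a negative binomial model will be fitted using the R library" edgeR, comparing treatment with placebo, with Benjamini-Hochberg-adjusted p of 0.05 or less. Neither description has a term for cell composition. Section 8.2.4.1 says "Whole blood and urine will be the biospecimens used for analyses".

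**The concern.** Whole blood is a mixture of cell types. A bulk methylation or expression value is an average over those types, weighted by their shares, so it moves when the shares move even if no cell changes. The protocol recognises this by measuring the mix, but section 9 never uses the measurement.

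What is at stake is interpretation. Section 4.1 hypothesises a whole-blood epigenome and transcriptome signature that predisposes to a pro-inflammatory state. With the planned output alone, a change in the neutrophil or lymphocyte share cannot be told apart from altered regulation within those cells, although the trial will hold the data needed to examine the difference.

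**Working it through.** **1. Does any planned analysis use the cell mix?**
- Methylation t-test (9.4.3): treatment only, and a t-test takes no covariate.
- edgeR model (9.4.3): treatment against placebo. edgeR could take covariates, but none is named.
- Linear mixed model for selected transcriptome and epigenome measures (9.2): period, sequence and carryover, with subject as a random effect. No cell proportions.
- Random Forest (9.4.3): transcriptome, epigenome and microbiome features only.
- Sorted-cell DNA/RNA (8.2): mentioned as something FACS makes possible. Section 9 has no such analysis, and 8.2.4.1 names whole blood and urine.
- Later document: section 9 says that there will be no formal SAP.

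So no planned analysis uses it.

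**2. Why the two explanations coincide.** Take two cell types with shares p and 1 − p and methylation a and b at a site. Whole blood reads M = p·a + (1 − p)·b.
- Only the mix changes: ΔM = Δp × (a − b).
- Only cell type A changes: ΔM = p × Δa.

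With a − b = 0.8 and Δp = 0.05, ΔM = 0.04. With p = 0.5 and Δa = 0.08, ΔM is also 0.04. The planned test sees the same difference.

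**3. How often could a composition-only site be declared?** The protocol gives no power or sample size for the omics endpoints, so there is no stated figure to reproduce here. All inputs below except the threshold and the numbers of participants are assumptions:
- between-cell methylation difference 0.8
- SD of the cell share 0.05 to 0.08
- within-person correlation of the share 0.3 to 0.7
- residual SD 0.02
- no within-cell change
- n = 28 (enrolled, section 12) or 40 (planned)

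Whole-blood differences for shifts of 3, 5 and 10 points are 0.03, 0.05 and 0.10 times 0.8, that is 0.024, 0.040 and 0.080.

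Hand check for n = 28 and share SD 0.05:
- SD per condition = √[(0.8 × 0.05)² + 0.02²] = √0.0020 = 0.0447.
- Two-sample standard error = 0.0447 × √(2/28) = 0.01195.
- Expected t = 2.0, 3.3 and 6.7 for 3, 5 and 10 points.
- Critical value at 9 × 10⁻⁸ with 54 degrees of freedom = 6.17.

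Only the 10-point shift reaches it. Simulation (20,000 trials per setting) gives these ranges over the assumed inputs:

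| Shift | Planned two-sample test, n = 28 | Planned test, n = 40 | Paired test, n = 28 | Paired test, n = 40 |
|---|---|---|---|---|
| 3 points | ≤0.01% | ≤0.05% | ≤0.09% | 0.01–1.0% |
| 5 points | 0–0.4% | 0–2.8% | 0.06–6.4% | 0.3–35% |
| 10 points | 3.5–72% | 25–99% | 8–98% | 42–100% |

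The paired columns matter because the analysis should respect the cross-over. In most settings pairing makes the test more sensitive, to composition shifts as well as to real within-cell effects.

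**4. What adjustment does.** In the same simulation, paired differences in methylation were regressed on paired differences in the share, and the intercept was tested. Rejection at the 0.05 level returned to 4.7–5.1%, and at 9 × 10⁻⁸ to essentially zero. This assumes that the share is measured without error and that nothing else drives both share and methylation.

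RNA-seq was not simulated. Its false-discovery rule is less strict than 9 × 10⁻⁸, so these percentages do not carry over to it.

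**The case against.** **The endpoint is whole blood by design.** Treatment order is randomised, so cell mix is a consequence of treatment (a mediator), not a confounder. The unadjusted contrast validly estimates the total effect on the declared endpoint, and a larger share of inflammatory cells could itself be part of a pro-inflammatory signature. This stands. A reader might infer that the planned comparison is biased or should be replaced. The documents do not support that, and the point is confined to what may be concluded from it.

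**The methylation threshold is severe.** A reader might also infer that any salt-driven shift in cell mix would be reported as an epigenome change. That goes too far: for shifts of up to 5 points the planned test would rarely declare such a site under the assumptions shown.

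**The protocol anticipates the problem.** Section 8.2 intends FACS to describe changes in cell profiles and to allow isolation of subtype DNA and RNA, which would be a more direct answer than a covariate. The intention is there, but no analysis in section 9 carries it out.

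**Adjustment has its own bias.** Conditioning on a variable affected by treatment can distort the direct effect if other factors drive both cell mix and the omics measure. This also stands, and it is why the adjusted model should not be the sole test for claiming regulation.

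**Conclusion.** The concern holds as a gap in interpretation for secondary endpoints. The leukocyte mix is measured at every visit for this purpose, and no planned methylation or RNA-seq analysis uses it. A composition shift could therefore be read as epigenetic or transcriptional regulation. That ambiguity follows from the averaging formula and needs no numerical assumption.

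How often it would produce declared sites is not known from the documents. Under the assumed inputs, composition-only methylation hits with the planned test are unlikely for shifts of 5 points or less (at most 0.4% with 28 participants, 2.8% with 40) and possible at about 10 points (3.5–72% and 25–99%). With a paired analysis and 40 participants, a 5-point shift reaches 35% in the least favourable setting. The size for RNA-seq is open. Urine RNA is outside the point.

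**What to change.** In section 9.4.3:

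1. Keep the unadjusted whole-blood comparison as the main result.
2. Replace the two-sample t-test with a per-site linear model that respects the cross-over pairing.
3. For whole-blood methylation and whole-blood RNA-seq (not urine), prespecify a supporting model that adds three to five main leukocyte proportions from the same visit, taken from FACS, or from the CBC differential where FACS is missing.
4. Report the effect of salt on the proportions themselves, and give unadjusted and adjusted estimates side by side.
5. Describe a result as consistent with within-cell regulation only if it persists after adjustment, and label it as conditional on measured composition.
6. State whether the subtype DNA/RNA mentioned in section 8.2 will be analysed. If so, add that analysis to section 9; if not, say so.

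Apart from any sorted-cell work under item 6, the cost is analysis wording and a second model run, with no new samples. The supporting model uses a few degrees of freedom, leaves out any effect that acts through cell mix, and can be biased by unmeasured factors that drive both cell mix and the omics measure. These limits should be stated with the results.

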### **9.2 SAMPLE SIZE DETERMINATION**

Data will be tested for normality using the Shapiro-Wilk test. Continuous variables will be described as mean  $\pm$  standard deviation (SD) if normally distributed. Variables with skewed distribution (i.e. aldosterone, BNP, etc.) were logarithmically transformed prior to analyses and are presented as median and interquartile range (IQR). Categorical variables will be expressed as numbers (percentages).

When data are normally distributed, comparisons between the treatment (sodium intake) and control (placebo) groups will be made using paired Student's t-tests, and when data are non-

[figure not shown]
normally distributed, the Mann-Whitney U test will be employed. Chi-square test will be used for categorical variables. Tests for sodium intake effect on the primary outcomes without correction for period effect will be done using Mann-Whitney test on the differences. Tests for period effect will be assessed using two-sample Wilcoxon tests on the differences between treatment groups, and tests for carry-over effect will be assessed by a two-sample Mann-Whitney test on the averages in the two treatment periods. Correlations were determined with Pearson's correlation coefficient.

Additionally, we will evaluate the effects of sodium intake on changes in blood pressure, 24-hr ambulatory blood pressure monitoring (ABPM), biochemical markers, vascular functions, and specific transcriptome and epigenome by using a linear mixed model, with subject as a random effect, thereby accounting for the period, sequence, and carryover effects and to model the various sources of intra-individual and inter-individual variability. All statistical tests will be two-sided and P values  $<0.05$  will be regarded as significant. Statistical analyses will be carried out using SAS software (SAS Institute, Inc., Cary, NC, USA).

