**Sample size and statistical power:** We expect to enroll and randomize a total of 40 eligible subjects for this protocol. The sample size is assessed to detect meaningful effects of sodium intake on the study's primary outcomes and secondary outcomes, including changes in vascular function (PWV m/s), sitting SBP and DBP (mm Hg), ABPM (mm Hg), biochemical markers (plasma aldosterone, pg/mL, brain natriuretic peptide (pg/mL), as well as epigenome, transcriptome, and microbiome under an assumption about the effect size, standard deviation outcomes, correlation of measurements within individual. We estimated that a sample size of 28 participants will be required in a cross-over study to detect changes in PWV between high salt intake and control groups of 0.6 m/s (estimates based on [Pimenta et al.](#) ), with 80% power and  $P < 0.05$ , assuming common SD of 0.9 m/s for high sodium intake and control groups, and correlation of 0.3 within subjects (Figure 2). Accounting for a potential of 20% dropout during the study, the sample size would be 34.

In addition, the estimated sample size will provide us with more than 80 percent power to detect a difference of 6 mm Hg (SD=9 mm Hg) in sitting SBP between sodium intake and the placebo treatment at 0.05 significance level (estimates based on [Tzemos et al.](#) ). Similarly, the proposed sample size would give more than 90% power to detect significant changes in plasma aldosterone (pg/ml) and brain natriuretic peptide (pg/mL) between high sodium intake and control at 0.05 significance level . The sample size calculation was performed using a paired *t* test assuming no carryover effect and no interactions between subjects, treatments, and periods.

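### The per-site methylation t-test in Section 9.4.3 ignores read depth and the crossover pairing, so it loses power at p < 9×10⁻⁸ by an amount the documents do not fix

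*Combined protocol and SAP*

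**What the plan says.** Section 9.4.3 of the combined protocol and SAP says that the salt effect on the epigenome "will be investigated through a two-sample t-test to identify methylation sites with significant methylation level difference between treatment and placebo". On the form of the data it adds: "Each methylation site will be treated as a continuous variable and salt intake will be treated as a nominal variable with two categories".

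The only coverage figures describe what the platform delivers: "At a minimum of 5X coverage and an average coverage of 30X", it "captures between 2.6 and 2.3 million methylation sites". No minimum depth for analysis is set; the text says only that "samples and methylation sites that passed all QC filters will be considered for the analysis". The per-site limit of p < 9×10⁻⁸ "will be applied to control for false positive findings; this threshold was derived from empirical work" on an array with fewer sites.

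No weights, read-count model or participant term appear in this analysis. By contrast, Section 9.4.2 normalises the microbiome counts and fits a negative binomial model, and Section 9.4.3 does the same for RNA-seq. Section 9.2 adds a mixed model with a random subject effect for selected transcriptome and epigenome measures, also without a depth term.

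**The concern.** A methylation level from sequencing is methylated reads divided by total reads. A sample with few reads at a site gives a much noisier level than one with many, and the depth is known for every sample and site. An unweighted t-test counts both equally.

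The trial is also a crossover, so a two-sample test leaves stable differences between people in the error term, although the design was chosen to remove them.

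With at most 40 people and a very small per-site alpha, only large differences can be found. Any avoidable noise therefore costs findings on this secondary endpoint.

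**Working it through.** **The plan's own figure.** Section 9.2 derives a sample size only for pulse wave velocity: 28 participants for 0.6 m/s, SD 0.9, correlation 0.3. The SD of the paired difference is 0.9 × √(2 × (1 − 0.3)) = 1.065. The noncentral t then gives 80.5% power at n = 27 and 82.0% at n = 28, so the figure is reproduced. It says nothing about methylation, for which no power is stated.

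**Inputs from the documents.**
- Sample size: "We expect to enroll and randomize a total of 40 eligible subjects for this protocol", hence 40 samples per condition. The Section 12 addendum reports 28 enrolled.
- Sidedness: "All statistical tests will be two-sided".
- Alpha: 9×10⁻⁸ per site.
- Coverage: minimum 5, average 30, as a platform description.

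**Assumed, because the documents are silent.** Spread of depth (negative binomial, mean about 30, values below 5 removed; a smaller size parameter means more uneven coverage), biological SD, and methylation of 50% to 80%.

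**Step 1: noise from reads.** The SD of a proportion is √(p(1 − p)/reads). At p = 0.5:
- 5 reads: √(0.25/5) = 0.224.
- 30 reads: √(0.25/30) = 0.091.

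The read-sampling variance differs by a factor of 30/5 = 6.

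**Step 2: cost of equal weights.** Variance per sample = biological SD² + p(1 − p)/depth. The cost ratio is mean(variance) × mean(1/variance), which is 1 if depth does not vary. As an example, take 10% of samples at 5 reads, 90% at 30, p = 0.5 and biological SD 0.05:
- At 5 reads: 0.0025 + 0.0500 = 0.0525.
- At 30 reads: 0.0025 + 0.0083 = 0.0108.
- Mean variance: 0.1 × 0.0525 + 0.9 × 0.0108 = 0.0150.
- Harmonic mean: 1/(0.1/0.0525 + 0.9/0.0108) = 0.0118.
- Ratio: 0.0150/0.0118 = 1.27.

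Results across the assumed coverage distributions:

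| Spread of depth | Biological SD | Ratio |
|---|---|---|
| Very uneven (size 1) | 3–5 points | 1.41–1.74 |
| Uneven (size 2) | 3–5 points | 1.29–1.49 |
| Fairly even (size 10) | 3–5 points | 1.08–1.13 |
| Any of these | 10 points | 1.02–1.20 |

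**Step 3: which spread counts.** The test runs one site at a time, so only variation in depth between samples at the same site matters. An overall average of 30 also hides variation between sites, which costs nothing here. If site means are allowed to vary and a separate within-site spread is assumed, the ratio is 1.03–1.04 with Poisson depth, 1.08–1.13 with within-site size 10, and up to 1.32 with more uneven depth.

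**Step 4: power.** At 9×10⁻⁸, 80% power in a two-sample test needs a standardised difference of 1.52 with 40 per condition (0.63 at alpha 0.05), or 1.90 with 28. Simulated reads for 40 participants, a difference of 15 points, within-site size 3 and weights estimated from the data give:

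| SD between people | As planned | Paired, unweighted | Paired, weighted |
|---|---|---|---|
| 5 points | 36% | 36% | 53% |
| 10 points | 7% | 38% | 56% |

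In a separate simulation with SD 10 points between people and 3 within, adding weights to the two-sample test only moved power from 8% to 10%.

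**Step 5: false positives.** At a nominal 5%, the planned test rejected 0.8% to 4.8% of true nulls, and the paired weighted test 5.4%. The rate was checked at 0.05, not at 9×10⁻⁸.

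**The case against.** The strongest reply is that the documents do not establish the size of the loss, and that much of it may be absent.

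- **5 reads is not a stated filter.** A reader might infer that sites enter with as few as 5 reads. The text gives 5X as the platform's capture condition, and the unspecified QC filters could ask for more. The inference is natural, because the plan justifies its threshold by millions of tested sites, which matches the count quoted at 5X. It is still an inference. Requiring 10 reads lowers the 1.29–1.49 to 1.16–1.30, so the loss shrinks but does not vanish. This stands as a limit.
- **A loss of 22–33% of samples is not the expected figure.** A reader might reach it from the 1.29–1.49 row (1 − 1/1.29 = 22%; 1 − 1/1.49 = 33%). It treats the whole spread around 30X as spread within a site, takes a small biological SD and assumes ideal weights. The documents support none of these.
- **Pairing may matter more than depth.** This is correct where people differ widely, as step 4 shows. With an SD of 5 points between people, pairing alone gains nothing and the depth weights supply the gain.
- **Section 9.2 already has paired tests and a mixed model.** It does, but Section 9.4.3 names a two-sample test for the site-by-site scan, and the mixed model is for selected measures and ignores depth. The sections need to agree.
- **A t-test on proportions is simple and valid.** That is accepted. The case for change is efficiency only.

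**Conclusion.** The point holds as a loss of efficiency on a secondary endpoint. The planned test discards two things the trial will already have: the depth of each measurement and the pairing.

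The cost of ignoring depth cannot be fixed from the documents. The variance ratio is about 1.0 to 1.3 if depth varies moderately between samples at a site, and up to about 1.7 if coverage is very uneven. It is close to 1 with even coverage or a biological SD of 10 points or more (1.02–1.20 at 10 points, the upper end only with very uneven coverage). All of these assume methylation of 50–80% and coverage averaging about 30. Ignoring the pairing costs little where people are alike and most of the power where they differ widely.

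A reader might also infer that the methylation findings would be unreliable. The check does not support that: the planned test was at or below its nominal error rate, and was conservative where people differed most. The risk is missed sites, not false ones. The change is worth making but not essential.

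**What to change.** In Section 9.4.3, replace the per-site two-sample t-test with a per-site model that has participant as block and period and salt as effects, and that takes depth into account. Two forms would do:
- a linear model with weights equal to 1/(estimated biological variance + p(1 − p)/depth), with p taken from the pooled level at the site, so that samples with 0% or 100% methylation do not get infinite weight in the absence of biological variance;
- beta-binomial regression on methylated and total reads.

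Report the depth-weighted mean difference with its 95% confidence interval. State the minimum depth and the number of samples a site needs to be analysed, and bring the mixed model in Section 9.2 into line.

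The cost is a change of wording and more computing time; depth comes with the sequencing output, so no new data are needed. Fits will be slower, and some low-coverage sites may not converge, so a fallback rule should be written down. Blocking also reduces the residual degrees of freedom (from 2 × 40 − 2 = 78 to 40 − 1 = 39 before the period term). At this threshold that can offset the gain from pairing at sites where people differ little. Calibration of the chosen model far out in the tail should be checked before unblinding.
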